## 2.4. Statistical Hypotheses

The primary objective of this study is to assess the PK, safety and tolerability of GSK3196165 in combination with MTX therapy in Japanese RA subjects. No formal hypotheses to be tested. Two-sided 90% confidence interval (CI) will be used for PK estimation.

### 3. PLANNED ANALYSES

#### 3.1. Final Analyses

The final planned analyses will be performed after the completion of the following sequential steps:

1. All subjects have completed the study as defined in the protocol.
2. All required database cleaning activities have been completed and final database release and database freeze has been declared by Data Management.
3. all criteria for unblinding the randomisation codes have been met.
4. Randomisation codes have been distributed according to RandAll NG procedures.

### 4. ANALYSIS POPULATIONS

Population	Definition / Criteria	Analyses Evaluated
All Screening	
 
• Comprise of all subjects who are given subject number and of whom data are collected at screening.
 
	
 
• Study Population
 

Randomised	
 
• All subjects who are randomized to treatment.
 
• Any subject who receives a treatment randomization number will be considered to have been randomized.
 
	
 
• Study Population
 

ITT	
 
• All subjects who are randomized to treatment and who receive at least one dose of study treatment.
 
	
 
• Study Population
 
• Efficacy
 
• Safety
 

PK	
 
• This population consists of all GSK3196165-treated subjects from whom PK samples are collected and analyzed.
 
	
 
• PK
 

Immunogenicity	
 
• The immunogenicity population will consist of all subjects in the ITT population, who had at least one immunogenicity assessment.
 
	
 
• Immunogenicity
 

**NOTES :**

- Please refer to Appendix 10: List of Data Displays which details the population to be used for each displays being generated.

#### 4.1. Protocol Deviations

- Important protocol deviations (including deviations related to study inclusion/exclusion criteria, conduct of the trial, patient management or patient assessment) will be summarised and listed.

- Protocol deviations will be tracked by the study team throughout the conduct of the study in accordance with the Protocol Deviation Management Plan.
  - Data will be reviewed prior to freezing the database to ensure all important deviations are captured and categorised on the protocol deviations dataset.
  - This dataset will be the basis for the summaries and listings of protocol deviations.
- A separate summary and listing of all inclusion/exclusion criteria deviations will also be provided. This summary will be based on data as recorded on the inclusion/exclusion page of the eCRF.

## 5. CONSIDERATIONS FOR DATA ANALYSES AND DATA HANDLING CONVENTIONS

Table 1 provides an overview of appendices within the RAP for outlining general considerations for data analyses and data handling conventions.

**Table 1 Overview of Appendices**

Section	Component
11.1	Appendix 1: Time & Events
11.2	Appendix 2: Assessment Windows
11.3	Appendix 3: Treatment States and Phases
11.4	Appendix 4: Data Display Standards & Handling Conventions
11.5	Appendix 5: Derived and Transformed Data
11.6	Appendix 6: Premature Withdrawals & Handling of Missing Data
11.7	Appendix 7: Multiple Comparisons & Multiplicity
11.8	Appendix 8: Model Checking and Diagnostics for Statistical Analyses.

## 6. STUDY POPULATION ANALYSES

### 6.1. Overview of Planned Analyses

The study population analyses will be based on the All Screening, Randomised and ITT population, unless otherwise specified.

Table 2 provides an overview of the planned study population analyses, with full details of data displays being presented in Appendix 10: List of Data Displays.

**Table 2      Overview of Planned Study Population Analyses**

Endpoint / Parameter / Display Type	Data Displays Generated		
	Table	Figure	Listing
Subject Disposition			
Subject Disposition for the Subject Conclusion Record	Y		
Reasons for Subject Withdrawal			Y
Treatment Status and Reasons for Discontinuation of Study Treatment	Y		Y
Screening Status and Reasons for Screen Failure	Y		Y
Subjects Who Were Rescreened			Y
Subjects Enrolled by Site ID	Y		
Subjects for Whom the Treatment Blind was Broken			Y
Planned and Actual Treatments			Y
Protocol Deviations			
Important Protocol Deviations	Y		Y
Subjects with Inclusion/Exclusion Criteria Deviations			Y
Populations Analysed			
Study Populations	Y		
Exclusions from ITT Population	Y		
Subjects Excluded from Any Population			Y
Demographic and Baseline Characteristics			
Demographic Characteristics	Y		Y
Baseline Efficacy Parameters	Y		
RF and ACPA	Y		Y
Age Ranges	Y		
Race and Racial Combinations	Y		Y [1]
RA Disease History	Y		Y
Substance Use	Y		Y
Prior and Concomitant Medications			
Medical Conditions			Y
Medications	Y		Y
Medications for RA prior to the Date of first dose	Y		
Medications for RA from the Date of first dose	Y		
Relationship of Medication Class, Dictionary Term and Verbatim Text			Y
Oral Corticosteroid by Visit	Y		
Change from Baseline in Oral Corticosteroid by Visit	Y		
Non-drug therapy			Y
Exposure and Treatment Compliance			
Exposure to Study Treatment	Y		Y
Exposure to MTX	Y		Y

**NOTES :**

- Y = Yes display generated.

[1] Listing of race.

### **6.1.1. Demographic Characteristics**

The following items will be summarized and listed by dose group in addition to those as standard.

- BMI
- Family history for Cardiovascular risk factor

### **6.1.2. Baseline Efficacy Parameters**

The following efficacy parameters at baseline will be summarized by dose group.

- DAS28(CRP, ESR)
- CRP, ESR
- Swollen Joint Count 66
- Tender Joint Count 68
- SDAI, CDAI
- Patient's Global Assessment of Arthritis
- Physician's Global Assessment of Arthritis
- Patient's Assessment of Arthritis Pain (current and past week's pain)
- HAQ-DI score
- FACIT-Fatigue

### **6.1.3. Rheumatoid Factor and Anti-cyclic Citrullinated Protein Antibody**

The number and percentage of RF positives and ACPA positives will be summarized.

### **6.1.4. RA disease history**

RA disease history will be summarized in form of disease duration categorical (< 2 years/  $\geq$  2 years) and as summary statistics (in month), RA functional class and time since start of RA symptoms. Disease duration and time since start of RA symptoms are defined in the Appendix 5.

### **6.1.5. Corticosteroid use**

Value and change from baseline in average daily prednisolone dose will be summarized and listed by visit. Average daily dose is defined in the Appendix 5.

### 6.1.6. Exposure

The extent of exposure to GSK3196165 and MTX will be evaluated by summarizing and listing the following items, respectively. These items are defined in the Appendix 5.

#### 6.1.6.1. GSK3196165

- The number of injections
- Cumulative dose in mg
- The duration of drug exposure in days

#### 6.1.6.2. MTX

- Overall average weekly dose

## 7. PRIMARY STATISTICAL ANALYSES

### 7.1. Pharmacokinetic Analyses

#### 7.1.1. Overview of Planned Pharmacokinetic Analyses

The PK analyses will be based on the PK population, unless otherwise specified.

Table 3 provides an overview of the planned analyses, with full details being presented in Appendix 10: List of Data Displays.

**Table 3      Overview of Planned Pharmacokinetic Analyses**

Endpoint / Parameter/ Display Type	Untransformed						Log-Transformed						
	Stats Analysis			Summary		Individual	Stats Analysis			Summary		Individual	
	T	F	L	T	F	F	L	T	F	L	T	F	F
Serum GSK3196165 Concentrations													
Serum Concentration				Y	Y	Y	Y						
PK Parameters													
Parameters				Y			Y				Y		
Dose Proportionality								Y				Y	

**NOTES :**

- T = Table, F = Figure, L = Listings, Y = Display generated.
- Stats Analysis = Represents TFL related to any formal statistical analyses (i.e. modelling) conducted.
- Summary = Represents TFL related to any summaries (i.e. descriptive statistics) of the observed raw data.
- Individual = Represents FL related to any displays of individual subject observed raw data.

#### 7.1.2. Drug Concentration Measures

Refer to Appendix 4: Data Display Standards & Handling Conventions (Section 11.4.3 Reporting Process & Standards).

### 7.1.3. Pharmacokinetic Parameters

#### 7.1.3.1. Deriving Pharmacokinetic Parameters

- Refer to Appendix 4: Data Display Standards & Handling Conventions (Section 11.4.3 Reporting Process & Standards).
- The PK parameters will be calculated by standard non-compartmental analysis according to current working practices and using WinNonlin (version 6.3 or higher).
- All calculations of non-compartmental parameters will be based on actual sampling times.
- PK parameters described in Table 4 will be determined from the serum GSK3196165 concentration-time data, as data permits.

**Table 4 Derived Pharmacokinetic Parameters**

Parameter	Parameter Description
AUCtau	
Area under the concentration-time curve from time zero (pre-dose in Visit 10) to 336 hr post-dose (Visit 12).
 
If a sampling time deviation occurred at nominal time 336 hours after administration (and <math>336 < t</math>), AUCtau will be calculated using the concentration at time 336 hours after administration post-dose estimated by the method of interpolation.
 
If nominal time 336 hours after administration <math>> t</math> (or if the concentration at time 336 hours after administration was below then limit of quantification), then the concentration (<math>y</math>) at time 336 hours after administration is estimated using <math>\lambda z</math> and last observed <math>C_t</math> according to the formula:
 $y = C_t(\text{obsr}) \times e^{-\lambda z(336-t)}$ 
Then the following equation will be used to calculate (<math>\text{AUCtau} = \text{AUC}(0-336)</math> after last-dosing) where <math>t</math> is the time of last quantifiable serum concentration.
 $\text{AUCtau} = \text{AUC}(0-t) + \text{AUC}(t-336)$ 
If <math>\lambda z</math> is not estimable, a <math>\text{AUC}(t-336)</math> is not calculated (when <math>336 > t</math>).
 
(NOTE: <math>\lambda z</math> is the apparent terminal phase rate constant.)

AUC(0-t)	
Area under the concentration-time curve from time zero (pre-dose in Visit 10) to the time of the last quantifiable concentration (<math>C(t)</math>) will be calculated by a combination of linear and logarithmic trapezoidal methods. The linear trapezoidal method will be employed for all incremental trapezoids arising from increasing concentrations and the logarithmic trapezoidal method will be used for those arising from decreasing concentrations (i.e., Linear Up/Log Down calculation method in Phoenix WinNonlin Professional).
 
NOTE: <math>C_t</math> is the last observed quantifiable concentration.

AUC(0-inf)	
Area under the concentration-time curve from time zero (pre-dose in Visit 10) extrapolated to infinity will be calculated as:
 $\text{AUC} = \text{AUC}(0-t) + C(t) / \lambda z$
%AUCex	
The percentage of AUC(0-inf) obtained by extrapolation (%AUCex) will be calculated as:
 $[\text{AUC}(0-\text{inf}) - \text{AUC}(0-t)] / \text{AUC}(0-\text{inf}) \times 100$

Parameter	Parameter Description
Cmax	Maximum observed concentration after last dosing (Visit 10), determined directly from the concentration-time data.
tmax	Time to reach Cmax, determined directly from the concentration-time data.
tlast	The time of the last measurable (positive) concentration.
t1/2	Apparent terminal half-life will be calculated as: $t1/2 = \ln 2 / \lambda_z$
lambda_z	The first order rate constant associated with the terminal (log-linear) portion of the curve.
lambda_z_lower	The lower limit on time for values to be included in the calculation of Lambda z.
lambda_z_upper	The upper limit on time for values to be included in the calculation of Lambda z.
#pts	The number of time points used in computing Lambda z.
R2	The goodness of fit statistic for the terminal elimination phase.

**NOTES:**

- Additional parameters may be included as required.

### 7.1.3.2. Statistical Analysis of Pharmacokinetic Parameters

The following PK statistical analyses will only be performed, if sufficient data is available (i.e. if subjects have well defined serum profiles).

Pharmacokinetic Statistical Analyses
Drug Concentration Measurements

 
Summary statistics, by dose group and nominal time point, will be calculated for the concentration of GSK3196165 in serum.
 
Individual serum concentration-time profiles will be plotted. Also median/mean profiles will be plotted. Each of the figures will contain one plot on the untransformed scale (i.e. a linear plot) and one plot on the loge-transformed scale (i.e. semi-log plot).
 
Mean/Median profiles by dose group will be plotted. Each of figures will contain one plot on the untransformed scale (i.e. a linear plot) and one plot on the log transformed scale (i.e. a log-linear plot).
 
Individual subject serum concentrations of GSK3196165 will be listed by dose group and nominal time. The items to be listed are center, subject, age, sex, race, dose, date, planned relative time, actual time, time deviation, actual relative time and concentration by dose groups.
 

Deriving and Summarizing Pharmacokinetic Parameters

 
The summary tables will be produced for the derived serum GSK3196165 PK parameter. Summary statistics will be calculated for each parameter by dose groups.
 
All the derived PK parameters for GSK3196165 will be listed, by subject and dose group. The items to be listed are center, subject, age, sex, race, dose, Cmax, Tmax, AUCtau, AUC(0-t), AUC(0-inf), %AUCex and t1/2.
 
Individual parameter, tlast, lambda_z, lambda_z_lower, lambda_z_upper, #pts and R2 will be listed. Summary statistics will not be calculated.
 
The steady-state will be examined graphically by plotting the Ctrough of Visit 2 - Visit 12 [Visit2 (Day 1), Visit4 (Day 8), Visit5 (Day 15), Visit7 (Day 29), Visit9 (Day 57), Visit10 (Day 71), Visit12 (Day 85)].
 

Pharmacokinetic Statistical Analyses	
Dose proportionality	

 
Dose proportionality of GSK3196165 for Cmax, AUCtau, AUC(0-t) and AUC(0-inf) will be evaluated using the power model defined as follows.
 
 $\log(Y_i) = \mu + \beta * \log(D_k) + \varepsilon_i$ 
 <math>Y_i</math> The measured response variable of PK parameter(Cmax, AUCtau, AUC(0-t) and AUC(0-inf)) for <math>i</math>th subject  <math>\mu</math> Intercept  <math>\beta</math> Slope of loge-transformed dose  <math>D_k</math> Dose (k=1: 45mg, 2: 90mg, 3: 180mg)  <math>\varepsilon_i</math> Random error following normal distribution <math>N(0, \sigma^2)</math> 
 
 
The power model will be fitted to loge-transformed PK parameters data using SAS Proc Mixed with loge-transformed dose as fixed effect. An estimate of the slope with corresponding 90% CI will be estimated from the power model to assess the degree of dose-proportionality (slope <math>\beta</math> around unity indicates dose-proportionality). Point estimates for the slopes of PK parameters with associated 90% CI will be presented.
 
If data permit, mean profile of Cmax, AUCtau, AUC(0-t) and AUC(0-inf) will be plotted. Each of the figures will contain one plot on linear and logarithmic scales.
 
	

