13. For women of child-bearing potential. S=serum; U=urine.
14. ESR measured locally.
15. PK sampling should be collected before dosing at the visits scheduled study treatment (GSK3196165/placebo). At the visits doesn't scheduled study treatments, it may be collected in any time during the visit. (Day 3, 74, 85, 106, 127, 155, and early withdrawal visit).
16. In consenting subjects.
17. In addition to these scheduled immunogenicity assessments, "event-driven" testing will also be employed for those subjects that experience anaphylaxis, serious hypersensitivity, or AEs related to study drug administration that led to withdrawal from the study (see Section 7.5 in the Protocol).
18. GSK3196165 or placebo must be administered on the same day each week  $\pm 1$  day for the first 5 weekly doses, thereafter on the same day EOW  $\pm 3$  days for bi-weekly doses.  
\* The Day 3 (Visit 3) blood sample must be drawn 2 days ( $\pm 1$  day is allowable) after the first dose, and the Day 74 (Visit 11) blood sample must be drawn 3 days ( $\pm 1$  day is allowable) after the last dose.  
\*\* HBV-DNA sample will be collected from all subjects, and HBV-DNA will be tested for only subjects with HBs Ab positive.

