### 11.10.7. Pharmacokinetic Tables

Pharmacokinetic : Tables					
No.	Population	IDSL / TST ID / Example Shell	Title	Programming Notes	Deliverable
Serum GSK3196165 Concentrations					
4.1.	PK	PK01	Summary of Serum GSK3196165 Concentrations		SAC
PK Parameters					
4.2.	PK	PK03	Summary of Derived Serum GSK3196165 Pharmacokinetic Parameters		SAC
4.3.	PK	PK05	Summary of Log-Transformed Derived Serum GSK3196165 Pharmacokinetic Parameters		SAC
4.4.	PK	PK_T1	Summary of Power Model Analysis for Dose Proportionality of GSK3196165 Pharmacokinetic Parameters	
 
• Cmax
 
• AUCTau
 
• AUC(0-t)
 
• AUC(0-inf)
 
	SAC

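### The AUC(0-t) slope for dose proportionality can exceed 1 under linear PK, because each subject's area stops at the last quantifiable sample

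*SAP*

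**What the plan says.** SAP 7.1.3.2 names four responses for the model log(Y) = μ + β·log(Dose), fitted over 45, 90 and 180 mg: "Dose proportionality of GSK3196165 for Cmax, AUCtau, AUC(0-t) and AUC(0-inf) will be evaluated using the power model defined as follows". On the output it says: "An estimate of the slope with corresponding 90% CI will be estimated from the power model to assess the degree of dose-proportionality". A slope near one is read as proportional. No acceptance limit is set, and SAP 2.4 says "No formal hypotheses to be tested".

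SAP Table 4 defines AUC(0-t) as "Area under the concentration-time curve from time zero (pre-dose in Visit 10) to the time of the last quantifiable concentration". In the same table AUCtau has a fixed window of 336 h after the Visit 10 dose, interpolated or extrapolated to that time if needed. Section 7.1.3.2 gives AUC(0-t) no common end time, no condition on tlast and no caution on interpretation. It lists tlast by subject, without summary statistics. All four slopes go into Table 4.4, "Summary of Power Model Analysis for Dose Proportionality of GSK3196165 Pharmacokinetic Parameters".

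The sampling days are the same at every dose. SAP Appendix 1, footnote 15, gives the samples at non-dosing visits as "Day 3, 74, 85, 106, 127, 155, and early withdrawal visit". After the last dose on Day 71, the scheduled samples therefore fall 3, 14, 35, 56 and 84 days later. Protocol 7.3 refers to the approved assay method but gives no limit of quantification.

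**The concern.** Under linear PK a 45 mg profile has the shape of a 180 mg profile at one quarter of the height. It therefore reaches a fixed assay limit no later than the 180 mg profile. If it reaches the limit at an earlier sample, the low-dose area covers a shorter time, and the slope then mixes dose proportionality with assay sensitivity.

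PK is a primary objective, and protocol 4.5 gives the assessment of linearity in Japanese subjects as one use of the dose range. A slope above 1 on AUC(0-t) could be read as more-than-proportional exposure when it reflects truncation. The plan does not say which of the four slopes governs if they disagree.

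**Working it through.** The plan states no expected slope or precision for this analysis, so there is no figure of its own to reproduce. The check asks what slope AUC(0-t) gives when PK is exactly linear.

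**Inputs from the documents**
- Doses on Days 1, 8, 15, 22, 29, 43, 57 and 71, with 10 subjects per arm.
- Post-dose samples as above, with the linear-up/log-down rule of SAP Table 4.
- Protocol Table 1, predicted human exposure at 180 mg: AUC(0-168) 1536 and AUC(0-336) 1930 µg·hr/mL. These figures reproduce the margins in protocol 4.5: 48963/1930 = 25.4 and 5644/1930 = 2.9.

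**Assumptions**
- A one-compartment SC model (Table 1 itself came from a two-compartment model).
- An absorption half-life of 1 to 4 days.
- The assay limit, which is varied.

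**Step 1: calibrate.** The elimination half-life that gives 1536/1930 = 0.796 is 12.9, 12.3 or 10.7 days for an absorption half-life of 1, 2 or 4 days. The 12.3-day case is used below, scaled so that AUC(0-336) at 180 mg is 1930/24 = 80.4 µg·day/mL.

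**Step 2: typical 45 mg concentrations.** At 0, 3, 14, 35, 56 and 84 days after the last dose they are about 1.16, 1.62, 1.11, 0.342, 0.105 and 0.022 µg/mL. The 180 mg values are four times these.

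**Step 3: 45 mg areas (µg·day/mL).** A rising segment is (C1 + C2)/2 × Δt. A falling segment is (C1 − C2)/ln(C1/C2) × Δt.
- 0–3 d: (1.16 + 1.62)/2 × 3 = 4.2
- 3–14 d: 11 × 0.51/ln(1.62/1.11) = 14.8
- 14–35 d: 21 × 0.768/ln(1.11/0.342) = 13.7
- 35–56 d: 21 × 0.237/ln(0.342/0.105) = 4.2
- 56–84 d: 28 × 0.083/ln(0.105/0.022) = 1.5

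The running totals are 19.0 to 14 d, 32.7 to 35 d, 36.9 to 56 d and 38.4 to 84 d.

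**Step 4: slope.** With equal numbers at three doses equally spaced on the log scale, β = ln(Y180/Y45)/ln 4.

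| Assay limit (µg/mL) | tlast 45 mg / 180 mg (d) | 180/45 ratio | AUC(0-t) slope |
|---|---|---|---|
| 0.02 or lower | 84 / 84 | 4.00 | 1.00 |
| 0.03–0.05 | 56 / 84 | 4 × 38.4/36.9 = 4.16 | 1.03 |
| 0.1 | 56 / 56 | 4.00 | 1.00 |
| 0.2–0.3 | 35 / 56 | 4 × 36.9/32.7 = 4.5 | 1.09 |

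The AUCtau slope is 1.00 in every row. The equality at 0.1 depends on the half-life: at 10.7 days the 45 mg profile stops at 35 d and the slope is 1.08.

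**Step 5: add variability.** Trials were simulated with 10 per arm and exact linearity. The CVs are assumed, between 30% and 45% on clearance and volume.

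| Assay limit (µg/mL) | Mean AUC(0-t) slope | 90% CI covers 1 |
|---|---|---|
| up to 0.01 | 1.00–1.01 | about 90% |
| 0.05 | 1.02–1.03 | about 89–91% |
| 0.1 | 1.05–1.06 | about 85–90% |
| 0.2–0.25 | 1.12–1.17 | about 83–85% |

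The sampling SD of the slope is about 0.20–0.25. At 0.25 µg/mL, with CVs of 40% on clearance, 30% on volume and 10% on the assay, the 90% CI lies wholly above 1 in 15.6% of trials. For AUCtau in the same trials the figure is 5.5%.

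**The case against.** The best defence is that the effect may not occur. If the assay is sensitive enough for every subject to be quantifiable at Day 155, all windows are equal and there is no bias. With samples this far apart, tlast can also coincide across doses at an intermediate limit. Up to 0.1 µg/mL the shift is well below sampling noise. This stands: a reader might infer that truncation must inflate the slope, but the documents do not establish it.

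The analysis also carries its own cross-check. Cmax and AUCtau do not depend on tlast in this way, and their slopes appear in the same table. An AUC(0-t) slope above 1 beside an AUCtau slope near 1 would be visible, and tlast is listed. This stands too. It limits the harm but does not justify the parameter, because no text tells the reader how to resolve a discrepancy. AUC(0-inf) is a weaker check: at a high limit, low-dose subjects may lack the late points needed for the terminal rate constant.

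Early withdrawal or missed late samples can shorten the window at any dose, so in a single trial of this size the net effect on the slope could go either way. The upward direction applies to the expected effect of assay truncation only. Finally, no decision hangs on the slope, since it is an estimate with no hypothesis attached.

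**Conclusion.** The point holds as a conditional weakness in one of four slopes. AUC(0-t) has no common window. If tlast is shorter at lower doses, its expected slope exceeds 1 under exact linearity, while AUCtau stays near 1. The size depends on an assay limit that the sponsor knows and the documents do not state. The shift is about nil up to 0.01 µg/mL, +0.02 to +0.06 at 0.05–0.1, and roughly +0.12 to +0.17 with coverage of about 83–85% at 0.2–0.25. These figures rest on the one-compartment model, the calibration to Table 1 and the assumed variability.

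Two stronger readings are not supported:
- **A slope of 1.3 or more.** This needs a limit near 0.5 µg/mL, above the 0.2 µg/mL in vitro inhibitory concentration in protocol 4.5. Results there are unstable: simulations with somewhat different settings gave mean slopes from about 1.19 to 1.33 and coverage from 59% to 82%. A typical 45 mg subject would have only Days 74 and 85 quantifiable after the last dose, and SAP 7.1.3.2 limits these analyses to subjects with well-defined profiles.
- **An improper addition.** AUC(0-t) is not among the PK variables in protocol 9.4.1. However, protocol section 9 leaves detail to the analysis plan, the notes to SAP Table 4 allow further parameters, and SAP 1.1 records the addition openly.

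**What to change.** In SAP 7.1.3.2, for dose proportionality, replace AUC(0-t) with an AUC over one fixed window common to all three doses. Choose a window that is quantifiable at 45 mg. Alternatively, drop AUC(0-t) from the power model, Table 4.4 and Figure 4.7 and keep it in the parameter listing. State that the proportionality conclusion rests on AUCtau, whose 336 h window is already fixed.

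If the AUC(0-t) slope is kept, label it supportive, state the assay limit, and show tlast by dose beside it.

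The cost is a line or two of text and two display entries, with no new data. The small downside is that one supportive slope is lost or relabelled.

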4. STUDY DESIGN

4.1. Overall Design

- This is a randomized, double-blind, parallel group, 3 dosage level, placebo-controlled, Phase 1/2 study with the objective to assess pharmacokinetics, safety, tolerability and efficacy of GSK3196165 for 12 weeks, in combination with methotrexate (MTX), in Japanese subjects with active moderate-severe RA despite treatment with MTX.
- Approximately 40 subjects will be randomized into the study (10 subjects in each treatment groups).

Figure 1 Study Design

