4.5. Dose Justification

A four-fold range of doses (45-180 mg), that are expected to result in largely non-overlapping exposures, are proposed for evaluation in this study. Study agent will be administered SC weekly for 5 injections, then every other week (EOW) injections. Dosing will use fixed doses, not based on body weight (i.e. mg/kg). This reflects the change to fixed doses in the Phase IIb study (Study 201755) and the proposed future dosing of GSK3196165 in the clinical setting.

Two Phase I studies in non-Japanese healthy volunteers showed that GSK3196165 was well tolerated up to 3.0 mg/kg following single IV dose and up to 2.0 mg/kg following single SC dose. Other Phase 1b repeat dose study in subjects with MS, GSK3196165 was also well tolerated up to 2 mg/kg following the EOW administration of the investigational product for 12 weeks (see GSK3196165 IB).

In case of the lowest eligible body weight in this study (i.e. 40 kg), which would be expected to result in the highest systemic exposure, the highest planned dose of 180 mg (SC) is equivalent to 4.5 mg/kg (SC). Based on the absolute bioavailability following SC administration (~ 44%) (see GSK3196165 IB), the systemic exposure at 4.5 mg/kg (SC)

is considered to be comparable with 1.98 mg/kg (IV), which is lower than the tolerable dose in Study MSC-1000, 3.0 mg/kg (IV).

Furthermore, the maximum dose proposed, 180 mg SC has been selected to allow ample margin to the no observed adverse effect level (NOAEL), and also a margin to the no observed effect level (NOEL) (the dose at which foamy alveolar macrophages were not observed in the 26-week rhesus monkey study). A dose of 180 mg SC is predicted to result in steady-state exposures which will allow a 25-fold margin to the NOAEL (50 mg/kg), where reversible minimal to mild foamy alveolar macrophages (considered non-adverse) were seen in the 26-week monkey toxicity study, with a 3-fold margin to the NOEL (5 mg/kg) (Table 1).

Table 1 Safety margins with 180 mg SC GSK3196165 relative to exposures to exposures in nonclinical toxicology studies

Study/ Species	Assessment	Dose (mg/kg/wk)	AUC(0-168) ^a (μ g.hr/mL)	AUC(0-336) ^b (μ g.hr/mL)	Fold difference		
					primates to human ratio	AUC(0-168) AUC(0-336)	
Rhesus Monkey 4 weeks IV	Week 4	5	4407	8814	2.9	NA	
		25	22250	44500	14.5		
		100 ^{c,d}	55101	110201	35.9		
Cynomolgus Monkey 13 week SC	Week 13	10	3149	6298	2.1	3.3	
		30 ^d	12765	25530	8.3		
		100 ^e	37797	75594	24.6		

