9.1. Hypotheses

The primary objective of this study is to assess the PK, safety and tolerability of GSK3196165 in combination with MTX therapy in Japanese RA subjects. No formal hypotheses to be tested. Two-sided 90% confidence intervals will be used for PK estimation.

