9.2. Sample Size Assumptions

The sample size is determined based on feasibility. A total of 40 subjects will be randomized in a 1:1:1:1 proportion to receive GSK3196165 doses of 45 mg, 90 mg, 180 mg or placebo.

[Table 4](#) provides the precision of percentage of subjects with specific adverse events in each group with 10 subjects.

Table 4 Precision of percentage of subjects with specific adverse events in each group with 10 subjects

Number of subjects	Number of particular safety events observed	Exact 95% confidence intervals
10	1	0.3% - 44.5%
10	2	2.5% - 55.6%
10	3	6.7% - 65.2%

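### The dose-proportionality model leaves out baseline body weight under fixed-mg dosing, which costs some precision and interpretability but causes no bias

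*SAP*

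**What the plan says.** SAP 7.1.3.2 regresses the log of each PK parameter (Cmax, AUCtau, AUC(0-t), AUC(0-inf)) on log dose at 45, 90 and 180 mg, "using SAS Proc Mixed with loge-transformed dose as fixed effect". The slope is reported with a 90% CI, and a value near 1 is read as proportionality; no margin is given. Protocol 9.1 confirms the interval ("Two-sided 90% confidence intervals will be used for PK estimation") and says that no formal hypothesis is tested.

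Protocol 4.5 specifies fixed doses rather than mg/kg. It takes the 40 kg subject, the lightest allowed, as the case "which would be expected to result in the highest systemic exposure". Inclusion criterion 9 sets that floor and no ceiling. Protocol 9.2 says "A total of 40 subjects will be randomized in a 1:1:1:1 proportion", which is 10 per arm, on grounds of feasibility. Protocol 6.2 mentions no stratification by weight.

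Body weight is measured at screening (Protocol 7.1 and 7.4.7). It is not in the power model or among the items that SAP 7.1.3.2 lists with the PK parameters. BMI is summarised by dose group (SAP 6.1.1). Population PK modelling is optional in both documents (Protocol 9.4.1, SAP 9.3), and no covariates are named.

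**The concern.** If lighter subjects have higher exposure at the same mg dose, weight is part of the between-subject variation in Cmax and AUC. The dose comparison is between separate arms of 10, so weight enters the slope in two ways. It enlarges the residual variance, which widens the CI. And if the 180 mg arm happens to be heavier or lighter than the 45 mg arm, that difference moves the slope away from 1 for a reason unrelated to dose.

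Protocol 4.5 gives assessment of PK linearity in Japanese subjects as one reason for the dose range, so this slope will be read. If the arms turn out unequal in weight, the plan provides no adjusted estimate, and one added after unblinding would be open to the charge of being chosen from the data.

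**Working it through.** **The plan's own figures.** No precision is stated for the slope. The figures that are stated reproduce:
- Protocol Table 4, exact 95% limits for 1, 2 and 3 events in 10: 0.3-44.5%, 2.5-55.6%, 6.7-65.2%.
- Protocol 4.5: 180 mg / 40 kg = 4.5 mg/kg SC; 4.5 x 0.44 = 1.98 mg/kg IV.

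**Inputs from the documents.** Doses 45, 90 and 180 mg; 10 subjects per active arm, so 30 in the model; two-sided 90% CI.

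**Assumed inputs (not in the documents).** Between-subject CV 30-50%; SD of log weight 0.15-0.20; exposure proportional to weight to the power -e, with e = 0.5-1.0.

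**1. Planned precision.** Log doses are ln 2 apart, so Sxx = 2 x 10 x (ln 2)^2 = 9.61, with square root 3.10. The residual SD on the log scale is s = sqrt(ln(1 + CV^2)), and the half-width is t(0.95, 28) x s / 3.10 with t = 1.701:
- CV 30%: 1.701 x 0.294 / 3.10 = 0.161
- CV 40%: 1.701 x 0.385 / 3.10 = 0.211
- CV 50%: 1.701 x 0.472 / 3.10 = 0.259

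**2. Chance weight differences.** The slope SD from weight alone is e x SD(log weight) / 3.10:
- Lowest: 0.5 x 0.15 / 3.10 = 0.024
- Highest: 1.0 x 0.20 / 3.10 = 0.065

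With equal arms, the slope is the 180 mg minus 45 mg difference in mean log exposure, divided by ln 4. A 10% difference in mean weight between those two arms therefore moves it by e x ln(1.1) / ln 4, which is 0.034 at e = 0.5 and 0.069 at e = 1. The 90 mg arm does not affect the slope.

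**3. Effect of adjustment.** Weight explains R2 = (e x SD(log weight) / s)^2 of the log-exposure variance. Adjustment multiplies the half-width by about sqrt(1 - R2) x sqrt(1 + 1/26) x 1.703/1.701. The last two factors, together about 1.02, are the price of estimating one more coefficient. Simulation of 40,000 trials per scenario agrees with these changes.

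| CV | SD log weight | e | R2 | Change in half-width |
|---|---|---|---|---|
| 50% | 0.15 | 0.5 | 0.03 | about +1% |
| 40% | 0.175 | 0.75 | 0.12 | about -4% |
| 40% | 0.20 | 1.0 | 0.27 | about -13% |
| 30% | 0.20 | 1.0 | 0.46 | about -25% |

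**4. Validity.** In the simulations both models have a mean slope of 1.00 and about 90% coverage over all randomizations. Given the realised weights, the planned interval does less well:
- Imbalance above 1 SD (about a third of trials): unadjusted coverage about 78-89% over the assumed range.
- Imbalance above 2 SD (about 5% of trials): about 52-87%.
- At CV 40%, SD 0.20 and e = 1: 83% and 69%.

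**The case against.** The strongest reply is that the planned analysis is valid. Randomization makes the unadjusted slope unbiased, and weight variation is already in the residual variance that sets the CI. That stands. A reader might infer that the slope is biased or its interval invalid; the calculation shows neither. Only precision, and coverage conditional on an observed imbalance, are affected.

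Nor does any decision turn on the slope, since there is no hypothesis, no margin and no sample-size target for it. That also stands and limits the severity.

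A reader might further infer that the protocol establishes weight as the driver of exposure. It does not. Protocol 4.5 uses the 40 kg subject as a worst case for a safety margin and quantifies no relation. The size of the problem therefore rests on assumptions, and their range includes no gain at all.

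Finally, BMI by dose group may reveal a body-size imbalance, and population PK might model weight. These mitigate but do not answer the point: BMI is not weight, a table does not adjust a slope, and the population analysis may never be done.

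**Conclusion.** The point holds as a cheap improvement of minor to moderate severity. The documents themselves supply fixed dosing, an expected weight-exposure direction, arms of 10 and a weight measurement that no planned PK analysis uses. The planned slope is sound on average, and nothing here invalidates it.

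Under the assumed CV, weight spread and exponent, weight contributes a slope SD of 0.024-0.065, against an unadjusted half-width of 0.16-0.26. Adjustment ranges from a negligible loss (about +1%) to a useful gain (about -25%), and middle cases are modest. The better argument for it is interpretability: the sponsor will have one realised allocation, and an adjusted slope fixed in advance would show whether a departure from 1 could be due to weight.

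**What to change.** Before database freeze, add to SAP 7.1.3.2 a prespecified model for Cmax, AUCtau, AUC(0-t) and AUC(0-inf):

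log(Y) = mu + beta x log(dose) + gamma x log(baseline weight) + error

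Take baseline weight as the latest pre-dose value, in line with SAP 11.4.2.1. Report beta with its 90% CI beside the planned unadjusted slope, so that the planned result stays visible. Summarise baseline weight by dose group for the PK population. If the codes have already been released, label the adjusted model post hoc.

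No new data are needed. The cost is one degree of freedom (27 instead of 28 with 30 profiles) and, if weight has no effect, a CI about 2% wider: sqrt(1 + 1/26) = 1.019. It is slightly more if fewer profiles are evaluable; with 24, for example, sqrt(1 + 1/20) = 1.025.
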